13. STUDY MEDICATION EXPOSURE

Exposure to study medication in days will be presented by treatment for the SAF analysis set. The date of first study medication inhalation, per treatment, will be taken from the Drug Exposure eCRF page for treatment period 1. The date of last study medication inhalation, per treatment sequence, will also be taken from the Drug Exposure eCRF page, based on the last end time of inhalation for the last treatment period of a patient.

Drug accountability i.e. the number of capsules used per treatment period, as measured on the Drug Exposure eCRF page will be summed to get the total number of capsules used and presented similarly to exposure, by treatment sequence for the SAF analysis set.

Document: Z:\RPL554\AZA40375\Biostatistics\Documentation\SAP\Verona RPL554-DP-201 SAP v2.0 – Part B

Author: [name] / [name]

Version Number: 2.0

Version Date: [08JUL2019]

Template No.: CS_TP_BS016 Revision 5

Reference: CS_WI_BS005

Effective Date: 01Apr2018

Copyright © 2009, 2010, 2012, 2016, 2018 IQVIA. All rights reserved. The contents of this document are confidential and proprietary to IQVIA Holdings Inc. and its subsidiaries. Unauthorized use, disclosure or reproduction is strictly prohibited.

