6.6. COMMON CALCULATIONS

Assessments assigned to treatment periods:

- Based on the day of assessment relative to the start date of each treatment period as defined by the first treatment administration for that specific treatment period:
 - Treatment period 1
 - Treatment period 2
 - Treatment period 3
 - Treatment period 4
 - Treatment period 5

For quantitative measurements, change from baseline will be calculated as:

- Test value at post-dose timepoint – baseline value.

For quantitative measurement values of FEV₁ and FEV₁ AUCs will be calculated based on:

- The highest FEV₁ reading from each assessment.
- The baseline value (average of the two pre-dose values [at 1-hour {±5 minutes} and immediately {within 5 minutes} } pre-dose) must be within ± 20% of the pre-albuterol value at Screening; otherwise, the patient will be a screen failure.

Peak effect will be calculated as:

- Maximum value in the first 4 hours after dosing.

Average effect will be calculated as:

- FEV₁ AUC divided by the length of the time interval of interest.

Document: Z:\RPL554\AZA40375\Biostatistics\Documentation\SAP\Verona RPL554-DP-201 SAP v2.0 – Part B

Author: [name] / [name]

Version Number: 2.0

Version Date: [08JUL2019]

Template No.: CS_TP_BS016 Revision 5

Reference: CS_WI_BS005

Effective Date: 01Apr2018

Copyright © 2009, 2010, 2012, 2016, 2018 IQVIA. All rights reserved. The contents of this document are confidential and proprietary to IQVIA Holdings Inc. and its subsidiaries. Unauthorized use, disclosure or reproduction is strictly prohibited.

Log-transformations will be performed on FEV₁ data:

- FEV₁ will be analyzed using multiplicative models, which means that data will be logged prior to analysis. The results will then be back-transformed to linear scale (treatment differences will thus be ratios of geometric means).

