13.1. DERIVATIONS

- Duration of exposure per treatment period (days) in Part B = date of last study medication administration, per treatment – date of first study medication administration, per treatment +1.
- Duration of exposure per treatment sequence (days) in Part B = Duration of exposure for period 1 + Duration of exposure for period 2 + Duration of exposure for period 3 + Duration of exposure for period 4 + Duration of exposure for period 5.
- Drug accountability (number of capsules) = Number of capsules dispensed – number of capsules returned by treatment period.

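### SAP Part B Sections 13 and 13.1 conflict on which dates define exposure per treatment; programmed as written, Section 13 would make the by-treatment exposure table wrong

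*SAP*

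**What the plan says.** SAP Part B Section 13 sets the presentation: "Exposure to study medication in days will be presented by treatment for the SAF analysis set". It then names two date sources. For the start: "The date of first study medication inhalation, per treatment, will be taken from the Drug Exposure eCRF page for treatment period 1". For the end: "The date of last study medication inhalation, per treatment sequence, will also be taken from the Drug Exposure eCRF page"; the date used is that of the final dose in whichever period came last for the patient. The start date is therefore labelled by treatment and the end date by sequence.

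Section 13.1 defines a duration for each treatment period as "date of last study medication administration, per treatment – date of first study medication administration, per treatment +1". The total for a sequence is the sum of the period values, beginning "Duration of exposure for period 1 + Duration of exposure for period 2 + Duration of exposure for period 3" and continuing through Period 5.

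Elsewhere, Section 6.6 assigns assessments to periods by reference to the "start date of each treatment period as defined by the first treatment administration for that specific treatment period". Section 6.1 likewise counts relative days from Day 1 of each treatment period.

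**The concern.** Part B is a five-period crossover, so for four of a patient's five treatments the Period 1 page records the first dose of a different treatment. Section 13.1 uses nearly the same term for its first date as Section 13 does, and Section 13 names no source for it other than the Period 1 page. Section 13 gives no per-treatment source for the last date at all. A programmer following Section 13 would count washout days, and days on other treatments, as exposure to the treatment being summarised.

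At stake is the table of exposure days by dose, which is part of the descriptive account of repeat dosing.

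**Working it through.** **Inputs**

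- Dosing in each period: 7 days, Day 1 to Day 7 (Protocol 5.1.2).
- Next Day 1: 7 to 10 days after Day 7 of the preceding period (Protocol 6.4.2.3).
- Five periods and ten sequences (SAP Part B 3.1 and Appendix 1).
- Duration: last date minus first date plus 1 (SAP Part B 13.1).

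**Step 1: the plan's own figures.** With each period's own dates, 13.1 gives 7 − 1 + 1 = 7 days per period and 5 × 7 = 35 days per completed sequence. As a check on the timeline, the components in Protocol 3.3 add to 7 + 1 + 35 + (4 × 7) + 4 = 75 days at least and 14 + 1 + 35 + (4 × 10) + 10 = 100 days at most. This matches the stated 75 to 100 days.

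**Step 2: distance between successive Day 1 visits, c.** Day 7 is 6 days after Day 1. Under Protocol 6.4.2.3, c = 6 + 7 = 13 to 6 + 10 = 16 days. The sum in Protocol 3.3 adds the 7 to 10 days to 7 full dosing days, which would give c = 7 + 7 = 14 to 7 + 10 = 17. Both are carried through.

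**Step 3: both Section 13 dates used as written.** The first date is Period 1 Day 1 and the last is Period 5 Day 7, so every treatment gets 7 + 4c days:

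- c = 13: 7 + 52 = 59
- c = 16: 7 + 64 = 71
- c = 14 to 17: 63 to 75

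All five treatments show the same value, including the one given in Period 1.

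**Step 4: Period 1 first date with each period's own last dose.** Exposure for the treatment in Period k is 7 + c(k − 1).

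| Period | c = 13 to 16 | Ratio to 7 days | c = 14 to 17 |
|---|---|---|---|
| 1 | 7 | 1.0 | 7 |
| 2 | 20–23 | 2.9–3.3 | 21–24 |
| 3 | 33–39 | 4.7–5.6 | 35–41 |
| 4 | 46–55 | 6.6–7.9 | 49–58 |
| 5 | 59–71 | 8.4–10.1 | 63–75 |
| Sum | 165–195 | 4.7–5.6 (against 35) | 175–205 |

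**Step 5: effect on each treatment's mean.** In the ten sequences of Appendix 1 each treatment appears twice in every period position. With equal allocation and no dropout, the Step 4 reading gives every treatment a mean of 165/5 = 33 to 195/5 = 39 days (35 to 41 with c = 14 to 17), against 7.

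**The case against.** The best defence is that 13.1 already gives the right answer. It is labelled as a duration per treatment period and adds five of them, which makes sense only if each period uses its own first and last dose. Sections 6.1 and 6.6 show that period-specific start dates are defined in the same document. The two Section 13 sentences also read naturally together as the start and end of the whole sequence, with the treatment label in the first a slip. A careful programmer would probably produce 7 days, and a table showing 20 to 71 days for a treatment dosed for 7 would be hard to miss.

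Much of this stands: it makes the overstatement conditional. It does not remove the conflict. The defence requires setting aside an explicit sourcing rule, and the SAP does not say that 13.1 prevails. Protocol 9.4.4 does not settle it, because it bases total exposure on compliance and dose group and names no date source.

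A reader might infer two stronger things. One is that exposure will be overstated several-fold; the period-based reading, which gives no error, rules out that certainty. The other is that tolerability conclusions would be distorted. The planned adverse event summaries are incidence counts and percentages (SAP Part B 16.1), with no exposure-adjusted rate, so these days are not a denominator for them. Nor would exposure always depend on where a dose fell in the sequence: that follows on the Step 4 reading only, since Step 3 gives every treatment the same value.

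**Conclusion.** There is a real inconsistency between Sections 13 and 13.1, of minor consequence. Following Section 13 literally gives 59–71 days for every treatment. The mixed reading gives 7 to 71 days depending on period, with a sequence sum of 165–195. The correct figures are 7 and 35. These ranges assume a patient who completes all five periods on schedule, with the next Day 1 falling 7 to 10 days after Day 7; counting 7 to 10 full days between periods raises them slightly, as shown. The 33–39 day mean further assumes equal allocation to sequences.

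Only the descriptive exposure summary in days is affected. Efficacy tests do not use these dates, and compliance rests on capsules dispensed and returned (SAP Part B 13.1 and 14).

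**What to change.** In SAP Part B Section 13, state that for each treatment the dates of first and last inhalation come from the Drug Exposure eCRF page of the treatment period in which that treatment was received, and that these dates feed the 13.1 formulas. Keep the Period 1 first dose and the last-period last dose only as the start and end dates of the sequence, and label both that way.

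This returns 7 days per treatment and 35 per completed sequence. The cost is a sentence or two of SAP wording, with no new data collection or change of method: Section 13 already draws on the Drug Exposure page for each treatment period.

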13.1. DERIVATIONS

- Duration of exposure per treatment period (days) in Part B = date of last study medication administration, per treatment – date of first study medication administration, per treatment +1.
- Duration of exposure per treatment sequence (days) in Part B = Duration of exposure for period 1 + Duration of exposure for period 2 + Duration of exposure for period 3 + Duration of exposure for period 4 + Duration of exposure for period 5.
- Drug accountability (number of capsules) = Number of capsules dispensed – number of capsules returned by treatment period.

14. STUDY MEDICATION COMPLIANCE

In Part B, patients will be dosed at the study center on the morning and evening of Day 1 and on the morning of Day 7. Patients will self-administer study medication for the other dosing times (i.e. on Days 2 through 6). Compliance will be assessed by recording the number of capsules dispensed and returned, as per drug accountability described in [Section 13](#).

15. EFFICACY OUTCOMES

15.1. PRIMARY EFFICACY

15.1.1. PRIMARY EFFICACY VARIABLE(S) & DERIVATION(S)

The primary efficacy variable is peak FEV₁ (measured in first 4 hours after morning dosing). This will be measured after dosing on Day 7 and is collected on the Spirometry Study measurements eCRF page. The primary efficacy endpoint is change from baseline in peak FEV₁.

Three acceptable readings are performed at each of the timepoints in first 4 hours after morning dosing on Day 7 (5, 15 and 30 minutes and 1, 1.5, 2 and 4 hours) and the highest of the 3 is used for analysis purposes. Hence, peak

Document: Z:\RPL554\AZA40375\Biostatistics\Documentation\SAP\Verona RPL554-DP-201 SAP v2.0 – Part B

Author: [name] / [name]

Version Number: 2.0

Version Date: [08JUL2019]

Template No.: CS_TP_BS016 Revision 5

Reference: CS_WI_BS005

Effective Date: 01Apr2018

Copyright © 2009, 2010, 2012, 2016, 2018 IQVIA. All rights reserved. The contents of this document are confidential and proprietary to IQVIA Holdings Inc. and its subsidiaries. Unauthorized use, disclosure or reproduction is strictly prohibited.

FEV₁ is derived as the highest of all these readings. Patients withdrawn after only one treatment period will not be included in the analysis.

Descriptive statistics (see [Appendix 1](#) [Programming conventions for outputs]) for FEV₁ will be presented for all patients assigned to FAS, at each assessment and change from baseline at each assessment. All summaries will be presented for each treatment group by day and timepoint. In addition, a figure (bar graph) representing mean change from baseline FEV₁ to peak FEV₁ by treatment will be presented, including the standard error of the mean.

Change from baseline FEV₁ to peak FEV₁ (over 4 hours) at Day 7 will be derived to test the hypothesis described in [section 15.1.3](#) with baseline defined as the average of the FEV₁ pre-dose assessment (-60 minutes and -5 minutes) collected on Day 1 of each treatment period. Peak FEV₁ at Day 7 is defined as the maximum post-dose value among the 5, 15, 30 minutes, 1, 1.5, 2 and 4-hour assessments collected at after morning dose on Day 7 of each treatment period.

15.1.2. MISSING DATA METHODS FOR PRIMARY EFFICACY VARIABLE(S)

No imputation will be applied.

15.1.3. PRIMARY ANALYSIS OF PRIMARY EFFICACY VARIABLE(S)

The primary efficacy objective of the study is to show that at least 1 RPL554 treatment group (RPL554 3000 μ g, RPL554 1500 μ g, RPL554 500 μ g, RPL554 150 μ g) will increase peak FEV₁ (change from Baseline) compared to placebo at Day 7 (measured in first 4 hours after morning dosing) by rejecting the null hypothesis described below at significance level $\alpha=0.05$ level (2-sided):

$$H_0: \mu_j = \mu_0 \text{ versus } H_1: \mu_j \neq \mu_0$$

where μ_j and μ_0 are the mean change from Baseline in peak FEV₁ at Day 7 (measured in first 4 hours after morning dosing) for 1 RPL554 treatment group (RPL554 3000 μ g, RPL554 1500 μ g, RPL554 500 μ g, RPL554 150 μ g) and placebo respectively.

Document: Z:\RPL554\AZA40375\Biostatistics\Documentation\SAP\Verona RPL554-DP-201 SAP v2.0 – Part B

Author: [name] / [name]

Version Number: 2.0

Version Date: [08JUL2019]

Template No.: CS_TP_BS016 Revision 5

Reference: CS_WI_BS005

Effective Date: 01Apr2018

Copyright © 2009, 2010, 2012, 2016, 2018 IQVIA. All rights reserved. The contents of this document are confidential and proprietary to IQVIA Holdings Inc. and its subsidiaries. Unauthorized use, disclosure or reproduction is strictly prohibited.

An ANCOVA will be used to test the hypothesis with change from baseline FEV₁ to peak FEV₁ (measured in first 4 hours after morning dosing) on Day 7 as response variable, and treatment and treatment period as fixed factors, patient as random and baseline FEV₁ as covariates. Analyses will be implemented using the SAS® procedure MIXED as follows:

```
PROC MIXED DATA = ...;
  CLASS USUBJID PERIOD TREATMENT;
  MODEL CHG = TREATMENT PERIOD BASELINE;
  RANDOM USUBJID;
  LSMEANS TREATMENT / CL DIFF;
RUN;
```

where CHG = difference in log (peak FEV₁ - baseline FEV₁)

TREATMENT = treatment group (RPL554 3000µg, RPL554 1500µg, RPL554 500µg, RPL554 150µg and placebo)

PERIOD = treatment period (treatment period 1, 2, 3, 4 and 5)

BASELINE = log (baseline FEV₁)

USUBJID = subject ID

The primary comparison will be the contrast (difference in least squares mean [LSMEAN]) between RPL554 3000µg and placebo on Day 7 (in first 4 hours after morning dosing).

Peak FEV₁ and the covariate, baseline FEV₁, will be log-transformed prior to analysis using natural logarithm. The difference between the two is log (peak FEV₁) – log (baseline FEV₁). Therefore, the LSMEAN statement between treatments in the above PROC MIXED will provide the log of the contrasts. Prior to presentations, the antilog of these point estimates and associated 95% confidence intervals will be performed, giving ratios of geometric means on the linear scale. The 2-sided p-value for the exponential (exp) least squares mean, exp(LSM), ratio between each of the 2 treatment groups and placebo will be reported.

Summary statistics for FEV₁ will be presented for baseline, peak on Day 7 (in first 4 hours after morning dosing) and change from baseline to peak by treatment group on patients with both assessments, on the original scale. A figure displaying the mean change from baseline FEV₁ over time by treatment and day will also be presented.

Document: Z:\RPL554\AZA40375\Biostatistics\Documentation\SAP\Verona RPL554-DP-201 SAP v2.0 – Part B

Author: [name] / [name]

Version Number: 2.0

Version Date: [08JUL2019]

Template No.: CS_TP_BS016 Revision 5

Reference: CS_WI_BS005

Effective Date: 01Apr2018

Copyright © 2009, 2010, 2012, 2016, 2018 IQVIA. All rights reserved. The contents of this document are confidential and proprietary to IQVIA Holdings Inc. and its subsidiaries. Unauthorized use, disclosure or reproduction is strictly prohibited.

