9.4.5 Efficacy/Pharmacodynamics

FEV₁ and FVC will be summarized as actual value and change from baseline using descriptive statistics over time for all treatments and both study parts.

The peak effect on FEV₁ during these time intervals will be computed as the maximum value in the 4 hours after dosing. The average effect (average FEV₁ AUC_{0-t}) will be calculated as the AUC divided by the length of the time interval of interest. For analysis of the peak, average and trough FEV₁, the change from baseline will be expressed as the parameter divided by the pre-dose Day 1 baseline value.

In Part A, computed pharmacodynamic parameters for FEV₁ will be compared between the treatments using analysis of covariance models with fixed factor treatment, and using the pre-dose baseline value as a covariate. In Part B, computed pharmacodynamic parameters (peak, AUC₀₋₄, AUC₀₋₁₂ and trough) for FEV₁ will be compared between the treatments using analysis of covariance models adjusting for treatment period and patient, and using the pre-dose Day 1 baseline value as a covariate. FEV₁ will be analyzed using multiplicative models, which means that data (dependent and baseline) are logged prior to analysis and the result then transformed back to the linear scale giving treatment differences as ratios of geometric means.

Primarily, active treatments will be compared to placebo. For RPL554 DPI, the high dose will first be compared to placebo, and if found statistically significant then the next lower dose will be compared to placebo, and if found statistically significant then the subsequent lower dose will be compared to placebo, and this procedure repeated for all doses. Secondarily, the different doses of RPL554 DPI will be compared. Results of the comparisons will be expressed as the mean geometric ratio with 95% confidence intervals and associated, 2-sided, p-value.

Onset of action will be calculated and summarized by treatment. In Part B, a Kaplan-Meier plot illustrating time to onset will be constructed and from the survival curves the median time to onset will be estimated. Placebo will not be included in summaries of onset of action.

In Part B, the average use of rescue medication during the treatment periods will be summarized by treatment group. In addition, all rescue medication used during the treatment visits (Day 1 in Part A and Days 1 and 7 in Part B) will be listed to assess the accuracy of the FEV₁ recordings.

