9.5 Determination of Sample Size

The sample size is determined for Part B. This is a complete block crossover study. Assuming a residual CV of 6% for peak FEV₁, 30 patients will give an 80% power to detect a pairwise difference in peak FEV₁ of 4.6%. Assuming a mean baseline FEV₁ of 1.5 L this will correspond to a difference of about 70 mL. To account for withdrawals, 36 patients will be randomized to Part A.

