15.2.3. ANALYSIS OF SECONDARY EFFICACY VARIABLES

The secondary variables will be analyzed by comparing the RPL554 treatment groups to each other and placebo by rejecting the null hypothesis described below at significance level $\alpha=0.05$ level (2-sided):

Document: Z:\RPL554\AZA40375\Biostatistics\Documentation\SAP\Verona RPL554-DP-201 SAP v1.0 – Part A

Author: [name]

Version Number: 1.0

Version Date: [19DEC2018]

Template No.: CS_TP_BS016 Revision 5

Reference: CS_WI_BS005

Effective Date: 01Apr2018

Copyright © 2009, 2010, 2012, 2016, 2018 IQVIA. All rights reserved. The contents of this document are confidential and proprietary to IQVIA Holdings Inc. and its subsidiaries. Unauthorized use, disclosure or reproduction is strictly prohibited.

$$H_0: \mu_j = \mu_0 \text{ versus } H_1: \mu_j \neq \mu_0$$

where μ_j and μ_0 are the mean change from Baseline for each parameter (Peak FEV₁, AUC_{0-4h} and AUC_{0-12h}) after single dose for each respective dose of RPL554 and placebo.

ANCOVA analyses will be implemented using the SAS® procedure MIXED as follows:

```
PROC MIXED DATA = ...;
  CLASS TREATMENT;
  MODEL CHG = TREATMENT BASELINE;
  LSMEANS TREATMENT / CL DIFF;
RUN;
```

where CHG = difference in log (parameter) – log (baseline parameter) i.e. log (parameter / baseline parameter)

TREATMENT = treatment group (Respective dose of RPL554, 150µg, 500µg, 1500µg, 3000µg and 6000µg and placebo)

BASELINE = log (baseline parameter)

The primary comparison will be the contrast (difference in least squares mean [LSMEAN]) between 6000µg RPL554 and placebo. The parameter value and its baseline will be log-transformed prior to analysis using natural logarithm. The difference between the two (log [parameter] – log [baseline parameter]) equals log (parameter / baseline parameter). The covariate, baseline parameter, will also be log transformed. Therefore, the LSMEAN statement between treatments in the above PROC MIXED will provide the log of the contrasts. Prior to presentations, the antilog of these point estimates and associated 95% confidence intervals will be performed, giving ratios of geometric means on the linear scale. The 2-sided p-value for the exponential (exp)least squares mean, exp(LSM), ratio between each of the 2 treatment groups and placebo will be reported.

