15.2.3. ANALYSIS OF SECONDARY EFFICACY VARIABLES

15.2.3.1. Analysis of Secondary Variables 1, 2, 3, 4, 5 and 6

The secondary variables listed above will be analyzed by comparing the RPL554 treatment groups to each other and placebo by rejecting the null hypothesis described below at significance level $\alpha=0.05$ level (2-sided):

$$H_0: \mu_j = \mu_0 \text{ versus } H_1: \mu_j \neq \mu_0$$

Document: Z:\RPL554\AZA40375\Biostatistics\Documentation\SAP\Verona RPL554-DP-201 SAP v2.0 – Part B

Author: [name] / [name]

Version Number: 2.0

Version Date: [08JUL2019]

Template No.: CS_TP_BS016 Revision 5

Reference: CS_WI_BS005

Effective Date: 01Apr2018

Copyright © 2009, 2010, 2012, 2016, 2018 IQVIA. All rights reserved. The contents of this document are confidential and proprietary to IQVIA Holdings Inc. and its subsidiaries. Unauthorized use, disclosure or reproduction is strictly prohibited.

where μ_j and μ_0 are the mean change from Baseline for each parameter for each respective dose of RPL554 and placebo.

ANCOVA analyses will be implemented using the SAS® procedure MIXED as follows:

```
PROC MIXED DATA = ...;
  CLASS USUBJID PERIOD TREATMENT;
  MODEL CHG = TREATMENT PERIOD BASELINE;
  LSMEANS TREATMENT / CL DIFF;
  RANDOM USUBJID;
RUN;
```

where CHG = difference in log (parameter – baseline parameter)

TREATMENT = treatment group (Respective dose of RPL554, 150 μ g, 500 μ g, 1500 μ g and 3000 μ g and placebo)

PERIOD = treatment period (treatment period 1, 2, 3, 4 and 5)

BASELINE = log (baseline parameter)

USUBJID = subject ID

The primary comparison will be the contrast (difference in least squares mean [LSMEAN]) between 3000 μ g RPL554 and placebo. The parameter value and its baseline covariate will be log-transformed prior to analysis using natural logarithm. The difference between the two log (parameter) – log (baseline parameter). Therefore, the LSMEAN statement between treatments in the above PROC MIXED will provide the log of the contrasts. Prior to presentations, the antilog of these point estimates and associated 95% confidence intervals will be performed, giving ratios of geometric means on the linear scale. The 2-sided p-value for the exponential (exp)least squares mean, exp(LSM), ratio between each of the 2 treatment groups and placebo will be reported.

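### Part B SAP 15.1.3 and 15.2.3.1: the definition of CHG under the model code puts the baseline subtraction inside the logarithm, against the text that follows it

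*SAP*

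**What the plan says.** The Part B SAP defines the model response in a legend under the code.

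- Section 15.1.3, primary endpoint (Day 7 peak FEV₁): "where CHG = difference in log (peak FEV₁ - baseline FEV₁", after which the bracket closes.
- Section 15.2.3.1, secondary variables 1 to 6: "where CHG = difference in log (parameter – baseline parameter", with the bracket closing in the same place.

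The paragraph after each code block gives a different response.

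- Section 15.1.3: "The difference between the two is log (peak FEV₁) – log (baseline FEV₁", closing bracket following.
- Section 15.2.3.1: "The difference between the two log (parameter) – log (baseline parameter", closing bracket following (the sentence lacks its verb).

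Both paragraphs then say that the antilog of the contrast gives ratios of geometric means.

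Two other places define the log-scale response.

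- Protocol 9.4.5: "the change from baseline will be expressed as the parameter divided by the pre-dose Day 1 baseline value". It adds that both the dependent variable and the baseline are logged before analysis.
- Part A SAP 15.2.3, the corresponding legend line: "where CHG = difference in log (parameter) – log (baseline parameter) i.e. log (parameter / baseline parameter", closing bracket following.

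Part B SAP 6.6 says "FEV₁ will be analyzed using multiplicative models, which means that data will be logged prior to analysis". That supports the difference of logs without stating it. Section 3.3 declares no change from the protocol analysis, and 15.1.2 and 15.2.2 allow no imputation.

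**The concern.** The legend is the line from which a programmer derives the response, and the paragraph below it contradicts it. This affects the primary endpoint and six secondary variables. It also affects the comparison of 3000 µg with placebo that opens the fixed testing sequence in 7.4.

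Taken literally, log(peak − baseline) has two consequences.

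- It has no value when the peak is at or below baseline. With no imputation, those records leave the analysis. If the drug raises FEV₁, more of them leave from placebo than from active treatment, so the loss depends on treatment.
- The antilog of the contrast is a ratio of millilitre increments. The output would still be labelled a ratio of geometric means of FEV₁.

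Morning trough (secondary variable 3) is the most exposed, because a placebo trough can lie close to baseline.

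**Working it through.** **1. The plan's own figure.** Protocol 9.5 states "30 patients will give an 80% power to detect a pairwise difference in peak FEV₁ of 4.6" per cent, with a residual CV of 6% and a mean baseline of 1.5 L. On the log-ratio scale:

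- SD = √ln(1 + 0.06²) = 0.0599
- SE of a pairwise contrast = 0.0599 × √(2/30) = 0.01548
- effect = ln 1.046 = 0.04497
- noncentrality = 0.04497 / 0.01548 = 2.906
- two-sided 5% critical t on 29 df = 2.045
- power = 80.2%

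Also 0.046 × 1500 mL = 69 mL, which matches the protocol's figure of about 70 mL. The stated power therefore reproduces on the ratio scale.

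**2. The narrative definition.** With log(baseline) as covariate, the model is

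log(peak) − log(baseline) = treatment + period + β·log(baseline) + patient + error.

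Moving log(baseline) to the right gives

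log(peak) = treatment + period + (β + 1)·log(baseline) + patient + error.

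The treatment contrasts and their standard errors are identical. The narrative therefore agrees with the protocol's logged dependent variable and logged baseline.

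**3. The printed definition: records lost.** Let X = ln(parameter/baseline), normal with the stated SD. A record is undefined when X ≤ 0. For a median placebo rise r and a true ratio of 1.046, the shares are

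- placebo: Φ(−ln(1 + r)/SD)
- active: Φ(−[ln(1 + r) + ln 1.046]/SD)

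The documents do not give r, and the 6% is a model residual CV, not the SD of X. Both are assumptions here. With SD 0.0599:

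- r = 3%: placebo Φ(−0.493) = 31.1%; active Φ(−1.243) = 10.7%
- r = 5%: placebo Φ(−0.814) = 20.8%; active Φ(−1.564) = 5.9%
- r = 10%: placebo Φ(−1.590) = 5.6%; active Φ(−2.340) = 1.0%

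At r = 5%, an SD of 4% gives about 11% and 1%, and an SD of 8% gives about 27% and 12%. For trough, if the median placebo change is zero (assumption), Φ(0) = 50% of placebo records are undefined whatever the SD.

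**4. The printed definition: what the antilog estimates.** The increment is baseline × (e^X − 1). With the same baseline distribution in both arms, the baseline cancels. Among the records that survive, the ratio is

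exp{ E[ln(e^X − 1) | X > 0, active] − E[ln(e^X − 1) | X > 0, placebo] }.

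Numerical integration with SD 0.0599, with increments shown for a 1.5 L baseline, gives:

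- r = 3%: 105.7 mL / 65.4 mL = 1.62
- r = 5%: 129.7 mL / 80.0 mL = 1.62
- r = 10%: 203.4 mL / 131.9 mL = 1.54

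The intended ratio is 1.046 in every row. At r = 5% the ratio is about 1.94 with SD 4% and about 1.44 with SD 8%. These are marginal geometric means, not fits of the planned mixed model.

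**The case against.** The strongest reply is that this is a typographical slip which the SAP itself resolves. The paragraph directly after each code block gives the difference of logs, as do Protocol 9.4.5 and the Part A legend. Section 3.3 rules out a deliberate departure. The phrase *difference in log* also suggests two logs, since the log of a difference is not a difference of logs. The harm arises only if a programmer ignores all of this, and its size rests on a placebo rise and an SD that the documents do not supply. All of that stands, and it limits the point to a correction of wording.

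It does not remove the point. The primary response is defined in two incompatible ways within one section, and the wrong one sits beside the code.

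Three stronger readings are tempting but not supported.

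- A reader might infer that Part B is planned on the wrong scale. The narrative, the protocol and the sample size calculation all use ratios.
- A reader might infer that every other sentence in the plan states the difference of logs. It does not. Section 6.6 also gives a generic change rule (test value minus baseline), and the summary statistics stay on the original scale. Neither defines the log-model response, although the generic rule could lead a programmer to subtract first and log afterwards.
- A reader might size the distortion by dividing the central-value increments. With SD 6% that exaggerates it at the smaller placebo rises, because the undefined records drop out.

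**Conclusion.** The point holds as an error in two definition lines of the Part B SAP, and it should be fixed. It is not an error in the intended analysis. Under the narrative definition, the estimand, the contrasts and the power of about 80% are unchanged.

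The consequences in steps 3 and 4 of the working arise only if the printed lines are coded, and the documents do not show which form was programmed. Treatment-dependent loss of records, and a contrast that is no longer a ratio of FEV₁ values, follow from the formula itself, provided that the drug raises FEV₁ and some records fall at or below baseline. The sizes are illustrations that move with the assumed placebo rise and SD.

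**What to change.** Change two lines.

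- Section 15.1.3: CHG = log(peak FEV₁) − log(baseline FEV₁).
- Section 15.2.3.1: CHG = log(parameter) − log(baseline FEV₁), i.e. log(parameter/baseline).

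This is the same form as in the Part A SAP. Naming baseline FEV₁ in the second line matches 15.2.1.1, which measures the change in the FEV₁ averages from baseline FEV₁. The missing verb in the sentence after the 15.2.3.1 code can be supplied at the same time. Section 6.6 needs no substantive change.

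If the derivation has already been programmed, confirm that it takes the two logs separately. The cost is an edit to the SAP and that check. No new data are needed, and sample size, power and planned contrasts stay as they are.
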